14.1. Overall Survival (OS)

Overall Survival (OS) is defined as the time from the date of first dose of study drug in the parent study until death due to any cause. Any patient not known to have died at the time of analysis will be right-censored based on the last recorded date on which the patient was - known to be alive, i.e. the latest of (i) the “Date of death or Last contact” (for those patients still alive) on the End of Study eCRF page and (ii) “Date patient last known to be alive” on the Survival Follow Up eCRF page. Also, to make sure that the last date patient was known to be alive is as accurate as possible, any date from the eCRF that indicates the patient is still alive will also be considered. The eCRF pages to be included in this check are: *AE/SAE, Prior and Concomitant Medication*, any page relating to patient Disposition, *Administration of Study Drug, Vital Signs, Electrocardiogram*, all Laboratory pages, and *Physical Examination*. The eCRF page dates that are not included in this check are: visit dates or signature dates or any other module that is not a true assessment date, e.g., sample processing dates. Date of death will be collected to assess OS only and will be listed according to treatment regimen.

OS will be calculated in number of months, calculated in two steps as:

- Time in days = (date of event – date of first dose in the parent study) + 1

- Therefore, time in months = time in days/ (365.25/12). In other words, 1 month = 30.4375 days.

Note here that time is calculated from the first dose of the treatment in the parent study.

15. Safety Outcomes

All summary outputs for safety outcomes will be based on the SAF analysis set. All safety tables and listings will be presented according to the [Appendix 1](#).

Unless otherwise stated, the overall observation period will be divided into 3 mutually exclusive segments as follows:

- Pre-treatment period: any time point prior to the first dose of IMCgp100 in the rollover study
- On-treatment period: from immediately after the first dose of study medication of the rollover study to 90 days after last dose of study medication in the rollover study.
- Post-treatment period: starting at Day 91 after last dose of study medication of this rollover study (including the 90-day Safety Follow-up period defined in Protocol Section 3.2)

For domains such as concomitant medications and adverse events, definitions of concomitance and treatment emergence are included in the associated sections of this SAP [section 12 and 15.1](#), respectively.

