## 2 RATIONALE

### 2.1 Study Rationale and Purpose

IMCgp100-401 is a rollover study that is designed to provide continued access to IMCgp100 for eligible patients with advanced melanoma who have previously participated in an IMCgp100 study (parent study). Parent studies that are eligible for patients to continue to receive IMCgp100 in this rollover study must have completed and satisfied its primary endpoints or have been terminated by the Sponsor for reasons other than safety.

Eligible patients for the rollover study will have tolerated IMCgp100 for a minimum of 4 weeks of dosing without significant toxicities that would preclude further dosing in the opinion of the principal investigator or of the Sponsor and have no evidence of unequivocal progressive disease (PD).

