## 3 STUDY DESIGN

### 3.1 Description of Study Design and Populations

This is a study of IMCgp100 conducted to provide continued access to IMCgp100 treatment for patients enrolled in a completed clinical study of IMCgp100. Patients enrolled in the rollover study must be currently receiving IMCgp100 within an IMCgp100 clinical study that has completed. Patients must meet all selection criteria defined in this rollover study [Section 5](#). Patients do not need to be re-assessed against the parent study entry criteria at the time of enrollment in the rollover study.

This rollover study will enroll patients who are currently receiving IMCgp100 treatment and for whom the parent IMCgp100 clinical study completes. At the time of parent study completion, the rollover study will enroll all patients actively receiving IMCgp100 treatment in the parent study in order to continue to provide patient access to treatment. Patients who enroll in the rollover study will, in the opinion of the investigator, continue to receive clinical benefit from treatment with IMCgp100. Patients who are receiving treatment as part of an ongoing, and not yet completed, study are not eligible to participate in the rollover study until the time of study completion.

At the time of rollover study entry, patients can continue to receive the current dose from the parent study or an alternative dose can be implemented with written agreement from the Sponsor. Doses higher than that in the parent in study will not be permitted.

- For patients from the IMCgp100-01 parent study the maximum dose will be the RP2D flat dose (50 mcg)

See [Table 6-1](#) in [Section 6.1](#) Study Treatment details in the rollover study. All patients must sign the rollover study consent form and be enrolled in the new study. All assessments will commence with Rollover Cycle 1. Safety assessments (physical examinations, clinical laboratory, and electrocardiogram [ECG] assessments, as well as continuous monitoring of AEs) will continue throughout the study at the described intervals. Patients will continue to receive IMCgp100 until loss of clinical benefit for the individual patient ([Section 6.6.1](#)), unacceptable toxicity as defined by the principal investigator or Sponsor, withdrawal of consent, loss to follow-up, or death.

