### 5.2 Inclusion Criteria

Patients eligible for inclusion in this study must meet **all** of the following criteria:

1. Patient is currently participating in an Immunocore-sponsored study of IMCgp100 and is actively receiving IMCgp100. Patient must have fulfilled all required assessments in the parent study (unless the study is being terminated)
2. Patient is currently receiving clinical benefit from the treatment with IMCgp100, as determined by the principal investigator from the parent study
3. Patient has demonstrated compliance with the parent study requirements, as assessed by the principal investigator and patient is able to comply with the necessary visits and assessments as part of the rollover study
4. Written informed consent must be obtained prior to enrolling in the rollover study and receiving the study treatment. If consent cannot be expressed in writing, then the consent must be formally documented and witnessed, ideally via an independent trusted witness

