2.2. Secondary Objectives

- To characterize the long-term safety (> 1 year dosing) and tolerability profile associated with treatment with IMCgp100
- To evaluate the incidence of anti-IMCgp100 antibody formation following multiple infusions of IMCgp100
- To estimate the overall survival (OS) in patients treated with IMCgp100.

3. Study Design

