3.3. Changes to Analysis from Protocol

The following are documented changes to analysis from protocol:

- Tables/Listings for change from baseline and shift tables are removed from the analysis for vital signs and ECG data. Note that vital signs will only be collected at baseline.

4. Planned Analyses

A final analysis after database lock is planned for this study.

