5.2. Full Analysis Set

The Full Analysis Set (FAS) comprises all patients assigned to treatment, who received at least 1 full or partial dose of IMCgp100. The FAS will be used for all demography, baseline characteristics, and OS data summaries.

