6.1. Reference Start Date and Study Day

Study Day will be calculated from the reference start date and will be used to show start/stop day of assessments and events.

Reference start date is defined as the day of the first dose of rollover study drug, (Day 1).

If the date of the event is on or after the reference start date, then:

- Study Day = (date of event – reference start date) + 1.

If the date of the event is prior to the reference start date, then:

- Study Day = (date of event – reference start date).

In the situation where the event date is partial or missing, the date will appear partial or missing in the listings, and Study Day and any corresponding durations will appear as missing in the listings.

Please note for survival, the first dose of the parent study will be used as reference instead.

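### The OS curve, timed from the first parent-study dose in patients who had to survive to rollover, overstates OS in patients treated with IMCgp100

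*SAP*

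**What the plan says.** - **Objective.** SAP 2.2 lists as a secondary objective: "To estimate the overall survival (OS) in patients treated with IMCgp100".
- **Time origin.** SAP 14.1 has OS "defined as the time from the date of first dose of study drug in the parent study until death due to any cause". SAP 6.1 makes this a deliberate exception to the rollover Day 1 reference date: "Please note for survival, the first dose of the parent study will be used as reference instead".
- **Censoring.** SAP 14.1 gives one rule, right-censoring at the date last known alive. Neither document mentions delayed entry, a landmark at rollover, or pooling with parent-study patients who did not roll over.
- **Analysis set.** SAP 5.2: "The FAS will be used for all demography, baseline characteristics, and OS data summaries". Membership requires a dose of IMCgp100 in the rollover study.
- **Who can enter.** Protocol 5.2 requires active treatment and this: "Patient is currently receiving clinical benefit from the treatment with IMCgp100, as determined by the principal investigator from the parent study". Protocol 5.3 excludes anyone permanently discontinued in the parent study for any reason. Protocol 2.1 says that eligible patients "will have tolerated IMCgp100 for a minimum of 4 weeks of dosing".
- **When they enter.** Protocol 3.1: "At the time of parent study completion, the rollover study will enroll all patients actively receiving IMCgp100 treatment in the parent study".
- **Estimator.** Protocol 9.7.1 plans Kaplan-Meier curves but gives no time origin. SAP 14.1 names no estimator. SAP 3.3 lists only this change from the protocol: "Tables/Listings for change from baseline and shift tables are removed from the analysis for vital signs and ECG data". The Kaplan-Meier plan therefore stands.

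**The concern.** A patient is in the OS set only if still alive and on drug at rollover. Parent-study patients who died or stopped before then are absent. An ordinary Kaplan-Meier curve from the first parent dose still counts every FAS patient as at risk from time zero, through an interval in which none of them could have an event. The curve stays at 100% until after the earliest rollover entry, and its later height depends on how long patients had already spent in the parent study. Because rollover opens when the parent study completes, that length depends partly on when each patient started.

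At stake is how a reader takes the result. Set against the objective in SAP 2.2, the curve would look like survival from the start of treatment in treated patients, and it would be too high. SAP 6.2 already declines to analyse change from the rollover baseline because patients had earlier IMCgp100 exposure. OS carries no comparable caution.

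**Working it through.** **Inputs.** The documents give no survival median, sample size or event count, so there is no figure of theirs to reproduce. They give one interval, the 4-week minimum: 28 / 30.4375 = 0.92 months. Everything else below is assumed.

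**Step 1: direction.** Let T be survival from the first parent dose and E the time of rollover entry. The FAS contains only patients with T > E. If E is unrelated to T, P(T > t | T > E) is at least P(T > t). Selecting on benefit raises it further, provided that benefiting patients live at least as long as others.

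**Step 2: a case that can be checked by hand.** Assume exponential survival with median 12 months, so λ = ln 2 / 12 = 0.05776, and entry uniform on 1 to 12 months.
- For t of at least 12, cohort survival is 11·exp(−λt) / D, with D = [exp(−λ) − exp(−12λ)] / λ = (0.9439 − 0.5) / 0.05776 = 7.685.
- At 12 months: 11 × 0.5 / 7.685 = 0.716, against a true 0.50.
- Median: exp(−λt) = 0.5 × 7.685 / 11 = 0.349, so t = 18.2 months, against a true 12.
- With risk-set entry at RC1D1 on the same axis (left truncation) the curve is exp(−λ(t − 1)), with median 13.0. The extra month is conditioning on survival to the earliest entry.

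**Step 3: other intervals.** Large-sample simulation, true median 12 months, 24 months of follow-up after RC1D1:

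| Entry (months) | Ordinary median | Left-truncated median |
|---|---|---|
| 4 weeks, all patients | 12.9 | 12.9 |
| U(1,3) | 14.0 | 13.0 |
| U(1,12) | 18.2 | 13.0 |
| U(1,36) | 26.6 | 13.0 |
| U(6,36) | 30.4 | 17.9 |

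The median from RC1D1 is 12.0 in every row, but only because the exponential has no memory.

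**Step 4: adding selection on benefit.** Assume 30% of patients have median 24 months and 70% have median 8 months (overall median 10.6). Entry is possible only while on treatment, which lasts 50–100% of survival in the first group and 10–60% in the second.

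| Entry (months) | Ordinary | Left-truncated | From RC1D1 |
|---|---|---|---|
| 4 weeks, all patients | 13.9 | 13.9 | 13.0 |
| U(1,3) | 17.2 | 17.1 | 15.2 |
| U(1,12) | 25.4 | 23.6 | 19.7 |
| U(1,36) | 39.8 | 26.4 | not reached |
| U(6,36) | 49.7 | 42.2 | not reached |

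In the first three rows left truncation removes only 0, 0.1 and 1.8 months (25.4 − 23.6 = 1.8). No column recovers 10.6.

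**Step 5: what the ordinary curve does describe.** Its median was compared with the enrolled cohort's actual median from first parent dose. For the four uniform entries, the exponential cases agree: 14.0, 18.2, 26.6 and 30.4. In the mixture, the cohort medians are 17.2, 25.4, 37.2 and 46.6, so the curve matches for the shorter intervals and runs about 3 months high for the two long ones.

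**The case against.** The strongest reply is that the curve is not wrong for the people in it. The OS set is the rollover FAS, so the objective's reference to treated patients could mean patients treated in this study. On that reading, ordinary Kaplan-Meier from the parent dose gives their total survival, and Step 5 bears this out closely. The origin is also stated openly in two SAP sections. This part stands: the defect lies in reading the curve as OS of treated patients, and a reader who infers that the curve misdescribes its own cohort goes too far.

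A second reply is that left truncation is a weak remedy. It assumes that entry is unrelated to later survival, yet entry here is selected on benefit. It can also be unstable: with true median 12 months and entry U(1,36), the left-truncated curve fell to zero with patients still observed in 14% of simulated trials of 10 patients and 5% of trials of 20. This stands too, so left truncation should only supplement.

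Third, restarting the clock at RC1D1 uses an administrative date for patients already on drug. That is true, and it is why the title must say what is estimated.

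Fourth, the output shells are not in the text reviewed and may carry a caveat. That cannot be checked, so nobody should infer that the curve will certainly appear without one. The SAP text itself has none.

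**Conclusion.** The point holds as one of estimand and labelling. An unqualified parent-origin Kaplan-Meier curve overstates OS in patients treated with IMCgp100, and the upward direction follows from the entry rules.

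The size is unknown. The only documented interval is the 4-week minimum, and it comes from the rationale in Protocol 2.1 rather than the listed criteria. In the exponential illustration the median is overstated by 0.9 months at that minimum (12.9 against 12) and by 6.2 months with entry over months 1 to 12 (18.2 against 12). A reader might infer a distortion of a year or more from the longest-interval rows, but those need intervals of up to 36 months, which the documents do not support.

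A reader might also infer that a better time origin or risk set recovers OS of all treated patients. It does not: those who died or stopped before rollover are not in the data.

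OS is a secondary objective, but Protocol 9.7 places its analysis under exploratory and SAP 6.5 plans no tests. The consequence is a descriptive result open to misreading, with no effect on error rates or decisions. It is worth correcting because the correction is cheap.

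**What to change.** In SAP 14.1 and 6.1:
1. Name Kaplan-Meier as the estimator.
2. Time the main OS curve from RC1D1. Title it as survival after rollover in patients selected for continued benefit, and show numbers at risk.
3. Optionally add a left-truncated curve on the parent-dose axis, with risk-set entry at RC1D1, as a supplementary display. Footnote that it assumes entry is unrelated to later survival and may be unstable where early risk sets are small.
4. Keep parent-origin times in listings. Show a parent-origin curve only if it is labelled as total survival of patients who rolled over, with survival guaranteed up to RC1D1.
5. State that none of these estimates OS of all patients treated with IMCgp100.

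The cost is SAP wording, titles and footnotes, and a small programming change. No new data are needed: SAP 13.1 already uses both the first parent dose date and the first rollover dose date. The downside is that reported survival becomes shorter and explicitly conditional.

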### 4.2 Secondary Objectives

- To characterize the long-term safety (> 1 year dosing) and tolerability profile associated with treatment with IMCgp100
- To evaluate the incidence of anti-IMCgp100 antibody formation following multiple infusions of IMCgp100
- To estimate the OS of patients treated with IMCgp100

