### 9.7 Exploratory Analyses

#### 9.7.1 Overall Survival

Date of death will be collected to assess OS only and will be listed according to treatment regimen.

The OS data will be presented graphically via Kaplan-Meier survival curves.

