4.1. Final Analysis

All final, planned analyses identified in this SAP will be performed by IQVIA Biostatistics following Sponsor Authorization of this SAP, Database Lock, and Analysis Sets and associated output shells.

5. Analysis Sets

Agreement and authorization of patients included/excluded from each analysis set will be conducted prior to the final analysis of the study.

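### Estimating OS is a secondary objective and the protocol plans Kaplan-Meier curves, but the SAP text specifies only a listing of death dates and does not declare the curve as dropped

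*SAP*

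**What the plan says.** **Objective.** Protocol 4.2 has "To estimate the OS of patients treated with IMCgp100", and SAP 2.2 has "To estimate the overall survival (OS) in patients treated with IMCgp100".

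**Protocol analysis.** Protocol 9.7.1 plans two outputs: a listing of death dates by regimen, and a figure: "The OS data will be presented graphically via Kaplan-Meier survival curves". It names no median, fixed-time survival probability or interval. It sits under Exploratory Analyses, although the objective is secondary.

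**SAP derivation.** SAP 14.1 defines OS as "time from the date of first dose of study drug in the parent study until death due to any cause". For censoring it says: "Any patient not known to have died at the time of analysis will be right-censored". The last date known alive is searched for across many eCRF pages. Time is converted to months: "In other words, 1 month = 30.4375 days".

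**SAP output.** The only OS output named in 14.1 is the listing: "Date of death will be collected to assess OS only and will be listed according to treatment regimen".

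**Related SAP sections.** Section 3.3, on changes from the protocol, covers only vital signs and ECG outputs. Section 5.2 says that OS summaries will use the FAS. Section 8 leaves the format and content of tables, figures and listings to template shells issued with the SAP.

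**The concern.** An objective to estimate survival calls for an estimate and some statement of its precision. SAP 14.1 prepares everything a time-to-event analysis needs and then stops before naming one. A listing of death dates makes no use of the censoring times or the conversion to months, and it gives no survival estimate.

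Two things are at stake. First, a programmer working from the SAP text alone could deliver the listing and leave a stated secondary objective without a result. Nothing in the SAP would show that the protocol's curve had been lost. Second, if a curve is produced from the shells without a specified method, its estimator, handling of entry and intervals would be settled outside the SAP. The handling of entry matters here because the OS clock starts before patients could enter this study.

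**Working it through.** **1. Protocol and SAP side by side**

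| Element | Protocol | SAP text |
|---|---|---|
| Objective: estimate OS | Yes (4.2) | Yes (2.2) |
| Listing of death dates | Yes (9.7.1) | Yes (14.1) |
| Kaplan-Meier curve | Yes (9.7.1) | Not mentioned |
| Median, fixed-time survival, interval | Not mentioned | Not mentioned |
| OS change declared | – | No (3.3) |
| Analysis set for OS summaries | FAS (9.2.1) | FAS (5.2), summaries undefined |

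In Protocol 9.7.1 the Kaplan-Meier sentence directly follows the listing sentence. SAP 14.1 carries over the listing sentence and not the one after it. Either the curve was dropped and 3.3 should say so, or it stands and 14.1 should specify it. The SAP text needs a correction in both cases.

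**2. The plan's own figure.** 365.25 / 12 = 30.4375 days per month, as SAP 14.1 states. This is correct and does not affect the point.

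**3. Illustrative precision.** The documents give no number of patients or deaths. Assume n = 10, 20 or 30, survival of 50% at some time point, and no censoring before it. The Kaplan-Meier estimate is then the simple proportion x/n. The exact (Clopper-Pearson) 95% limits are the 0.025 quantile of Beta(x, n − x + 1) and the 0.975 quantile of Beta(x + 1, n − x).

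| x/n | Lower | Upper | Width (points) |
|---|---|---|---|
| 5/10 | 18.7% | 81.3% | 62.6 |
| 10/20 | 27.2% | 72.8% | 45.6 |
| 15/30 | 31.3% | 68.7% | 37.4 |

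The log-log interval proposed in the fix is similar. Its limits are S^exp(±1.96·se), with se = √(S(1 − S)/n) / (S·|ln S|).

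- n = 10: se = 0.1581 / 0.3466 = 0.456, limits 18.4% and 75.3%, width about 57 points.
- n = 30: se = 0.0913 / 0.3466 = 0.263, limits 31.3% and 66.1%, width about 35 points.

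Censoring would generally widen these intervals.

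**4. Effect of the time origin.** Protocol 5.1 requires patients to be still receiving IMCgp100 at rollover entry, when the parent study is completing. SAP 14.1 starts the clock at first parent-study dose. Let L be a patient's time from that dose to rollover entry, and X the time to death or censoring. No patient in the FAS can have died before L.

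- An ordinary Kaplan-Meier estimate counts a patient as at risk at time t if X ≥ t.
- With delayed entry, a patient is at risk only if L < t ≤ X.

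The ordinary risk set n(t) is therefore never smaller. Each factor 1 − d(t)/n(t) is never lower, and the ordinary curve never lies below the delayed-entry curve. The direction of the bias is upward. Its size cannot be calculated, because the documents give neither parent-study durations nor numbers of deaths.

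**The case against.** **The shells may contain the curve.** SAP 8 defers content to shells that are not available here, and SAP 5.2 presupposes OS summaries. The listing sentence is carried over from the protocol, where it stands beside the Kaplan-Meier plan, so it need not be exclusive. A reader might infer that the SAP has removed the curve or that no OS estimate will be produced. The documents do not show that. They show only that the SAP text specifies none. What remains is that the estimator, interval method and time points belong in the SAP, not only in a shell.

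**SAP 4.1 does not confine the outputs.** It begins "All final, planned analyses identified in this SAP will be performed", and a reader might take this to exclude anything not named in the SAP. The rest of the sentence says who performs the analyses and after which steps, including the output shells. It sets no limit on what may be produced.

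**The protocol promised curves only.** This stands. The possible undeclared departure is the curve alone. The missing median and interval are a gap in both documents, not a breach of the protocol.

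**The study is descriptive.** There is no hypothesis testing (SAP 6.5) and no formal sample size (Protocol 9.9). The endpoint that Protocol 4.4 pairs with the OS objective is date of death, which a listing does report. This argues against treating the point as critical, but both objectives still say that OS will be estimated. If the sponsor thinks the numbers too few, the SAP can say so openly.

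**Conclusion.** The point holds as a gap in specification. OS is to be estimated, the protocol plans a Kaplan-Meier curve, and the SAP text provides only a listing without declaring a change. It should be corrected, but it concerns a secondary objective and does not touch the primary safety analysis.

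The size can only be illustrated. At 50% survival without censoring, the exact 95% interval would be about 37 points wide with 30 patients and 63 points with 10. These patient numbers are assumptions, and the documents do not say how large the cohort is.

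A reader might also infer that adding an ordinary Kaplan-Meier curve would settle the matter. It would not. From first parent-study dose, such a curve would be biased upward because patients had to survive to rollover entry, and an interval around it would lend apparent precision to a biased estimate.

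**What to change.** **Add to SAP 14.1:** OS in the FAS will be estimated by the Kaplan-Meier method. The outputs will be the curve with numbers at risk, the numbers of deaths and censored patients, and, where estimable, the median and survival probabilities at stated times, each with a 95% confidence interval on the log-log scale.

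**State the handling of entry.** Either keep first parent-study dose as the origin and analyse with delayed entry (left truncation) at rollover entry, or measure time from the first rollover dose. In both cases, state as a limitation that patients were selected for being alive, on treatment and judged to be benefiting when the parent study completed. Delayed entry deals with the survival time before entry but not with that selection.

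**Alternative.** If the numbers are considered too few, declare in SAP 3.3 that OS will be listed only, give the reason, and reword the objective in both documents.

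**Also reconcile** the status of OS, which is secondary in Protocol 4.2 but analysed under the exploratory heading of Protocol 9.7.

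**Cost.** A few lines of SAP text, one table and one figure. No new data are needed, because SAP 6.1 and 13.1 already use both first-dose dates. With delayed entry, the programming must use a procedure that accepts entry times. The intervals will be wide, and early risk sets under delayed entry may be small, so the early part of the curve may be unstable or not estimable.
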